6.6 Prior and Concomitant Medications

The latest World Health Organization Drug Dictionary (WHODD) version around the time of Database Lock will be used to code the recorded medications to Anatomical Therapeutic Chemical (ATC) level and standardized (generic) medication name.

Prior medications are those taken with a stop date prior to the start of the Treatment Period. Concomitant medications are those with a start date and time on or before the end of the Treatment Period and a stop date on or after the start of the Treatment Period, including prior medications that are ongoing at the start of the Treatment Period. Analogous logic is used to assign concomitant medication to Period 1 and Period 2. Post-treatment medications are those with a start date after the end of the Treatment Period.

See [Section 8.3](#) below for details on how to identify prior vs. concomitant when the start/end dates for the medication usage are partial dates or missing.

6.7 Primary Efficacy Endpoint

The primary endpoint of the study is HiSCR75, the proportion of subjects achieving at least a 75% reduction from baseline in the total AN count, with no increase from baseline in abscess or draining fistula count, at Week 12.

The proportion of subjects achieving HiSCR75 will be defined as meeting all 3 criteria below at a specific assessment:

- $[(\text{AN count at baseline} - \text{AN count at current visit}) / \text{AN count at baseline}] \times 100\% \geq 75\%$
- Abscess count at baseline \geq abscess count at the current visit

- Draining fistula count at baseline \geq draining fistula count at the current visit

where AN count is abscess count + inflammatory nodule count, and abscess count, inflammatory nodule count and fistula count are summed across all regions and are inclusive of all abscesses, inflammatory nodules and fistula that have previously undergone localized surgical or medical intervention and are no longer present.

6.7.1 Estimand for Primary Endpoint

The primary estimand is defined through the 5 attributes described in the following sections.

6.7.1.1 *Treatment Condition of Interest*

The primary treatment condition of interest is izokibep versus placebo.

6.7.1.2 *Population of Interest*

The population of subjects is those who are 18 years and older with moderate to severe HS (HS lesions present in ≥ 2 distinct anatomic areas, 1 of which must be Hurley Stage II or Hurley Stage III, and a total AN count of ≥ 5) who meet all inclusion criteria and exclusion criteria.

6.7.1.3 *Variable of Interest*

The endpoint for each subject to address the clinical question is achievement of HiSCR75 after 12 weeks of treatment.

6.7.1.4 *Intercurrent Event (ICE)*

The treatment policy strategy approach will be used in general. Thus, all subjects will be included using observed data at Week 12 regardless of treatment discontinuation, concomitant medication/rescue medication, protocol deviations, or other actions.

Subjects who receive antibiotic therapy that could affect HS will be included in the primary analysis by assigning non-response at subsequent timepoints. A list of all oral antibiotic therapy that results in such imputation will be finalized after review of all oral antibiotic therapy received by any subject and before unblinding of the study, and will include tetracycline, clindamycin, and possibly other products. Similarly, subjects who discontinue treatment due to an AE or lack of efficacy, and subsequently have missing efficacy responses, will be included by imputing non-response.

Multiple Imputation will be used to handle other types of missing data as described in [Section 9.5](#).

6.7.1.5 *Population Level Summary*

The population level summary is the response rate, or proportion of subjects who meet HiSCR75 after 12 weeks of treatment.

6.8 Secondary Efficacy Endpoints

The secondary efficacy endpoints are defined in [Table 4](#):

Table 4: Secondary Efficacy Endpoints

Endpoint	Derivation
HiSCR90 at Week 12	At least 90% reduction from baseline in the total AN count, with no increase from baseline in abscess or draining fistula count at Week 12. Must meet all 3

	criteria as described for the primary endpoint replacing 75% with 90%
HiSCR100 at Week 12	At least 100% reduction from baseline in the total AN count, with no increase from baseline in abscess or draining fistula count at Week 12. Must meet all 3 criteria as described for the primary endpoint replacing 75% with 100%
HiSCR50 at Week 12	At least 50% reduction from baseline in the total AN count, with no increase from baseline in abscess or draining fistula count at Week 12. Must meet all 3 criteria as described for the primary endpoint replacing 75% with 50%
HS Flares Through Week 12	
$\geq 25\%$ increase in AN count with a minimum increase of 2 AN relative to baseline, i.e. subject must meet all the following criteria at Week 12:
 
 • $(\text{AN count at current visit} - \text{AN count at baseline}) / \text{AN count at baseline} \times 100\% \geq 25\%$ • $\text{AN count at current visit} - \text{AN count at baseline} \geq 2$ 
A subject will be counted as having HS flare if they have a HS flare at any assessment after baseline, up to and including the assessment at Week 12 (including scheduled and unscheduled visits and early termination visits)

Change in DLQI from baseline to Week 12	(DLQI score at current visit – DLQI score at baseline) at each post baseline visit until Week 12 DLQI comprises 10 items arranged in 6 categories: symptoms and feelings (questions 1 and 2), daily activity (3 and 4), leisure (5 and 6), work or study (7), interpersonal relationships (8 and 9), and treatment (10). The total score can vary from 0 (no impact) to 30 (maximum impact).
AN count of 0, 1, or 2 at Week 12	Observed values of 0,1, or 2 for AN count (abscess count + inflammatory nodule count)
Change in pain score from baseline in NRS Patient Global Assessment of Skin Pain at its worst at Week 12	NRS in Patient Global Assessment of Skin Pain at its worst is the answer from Question on the eCRF: In the last 24 hours, which number best describes your skin pain at its WORST due to your HS? The answer is in the range of 0 (No skin pain) to 10 (Skin pain bad as you can imagine). The skin pain score at each visit will be calculated using average of daily scores among the 7 days up to and including the day of visit, with a minimum of 4 days (consecutive or non-consecutive) with scores required. The skin pain at baseline will be calculated using average of daily scores among the 7 days up to and including the first study drug administration day, with a minimum of 4 days with

	scores required. For any visit, if Patient Global Assessment of Skin Pain at its worst is available for 3 or few of the 7 days up to and including the day of visit, the pain score will be missing for analysis.
--	---

6.8.1 Estimand for Secondary Efficacy Endpoints

Estimands for secondary efficacy endpoints are defined in [Table 5](#), below:

Table 5: Estimands for Secondary Efficacy Endpoints

Endpoint	Estimand Attribute	Explanation
HiSCR90 at Week 12	Treatment Condition of Interest	izokibep versus placebo
	Population of Interest	Subjects with HS who meet all inclusion/exclusion criteria
	Variable of Interest	Percentage of subjects achieving HiSCR90 at Week 12
	Intercurrent Event	Treatment policy strategy, in general, with all subjects included in the analysis regardless of treatment discontinuation, concomitant medication/rescue medication, protocol deviations, or other actions. Subjects who receive antibiotic therapy that could affect HS will be included in the primary analysis by assigning non-response at subsequent timepoints. Multiple imputation and non-response imputation will be used to handle certain other types of missing data, analogously to the primary endpoint.
	Population Level Summary	Response Rate of HiSCR90 at Week 12 (Yes/No)
HiSCR100 at Week 12	Treatment Condition of Interest	izokibep versus placebo
	Population of Interest	Subjects with HS who meet all inclusion/exclusion criteria
	Variable of Interest	Percentage of subjects achieving HiSCR100 at Week 12
	Intercurrent Event	Treatment policy strategy, in general, with all subjects included in the analysis regardless of treatment discontinuation, concomitant medication/rescue medication, protocol deviations, or other actions. Subjects who receive antibiotic therapy that could affect

		HS will be included in the primary analysis by assigning non-response at subsequent timepoints. Multiple imputation and non-response imputation will be used to handle certain other types of missing data, analogously to the primary endpoint.
	Population Level Summary	Response Rate of HiSCR100 at Week 12 (Yes/No)
HiSCR50 at Week 12	Treatment Condition of Interest	izokibep versus placebo
	Population of Interest	Subjects with HS who meet all inclusion/exclusion criteria
	Variable of Interest	Percentage of subjects achieving HiSCR50 at Week 12
	Intercurrent Event	Treatment policy strategy, in general, with all subjects included in the analysis regardless of treatment discontinuation, concomitant medication/rescue medication, protocol deviations, or other actions. Subjects who receive antibiotic therapy that could affect HS will be included in the primary analysis by assigning non-response at subsequent timepoints. Multiple imputation and non-response imputation will be used to handle certain other types of missing data, analogously to the primary endpoint.
	Population Level Summary	Response Rate of HiSCR50 at Week 12 (Yes/No)
HS Flares Through Week 12	Treatment Condition of Interest	izokibep versus placebo
	Population of Interest	Subjects with HS who meet all inclusion/exclusion criteria
	Variable of Interest	Change in HS flares after 12 weeks of treatment
	Intercurrent Event	Treatment policy strategy, with all subjects included in the analysis regardless of treatment discontinuation, concomitant medication/rescue medication, protocol deviations, or other actions. All subjects with missing abscess, inflammatory nodule, and draining tunnel counts will be

		included using multiple imputation, analogously to the analysis of the primary endpoint. Multiple Imputation described in Section 9.6.1 . Subjects who receive antibiotic therapy that could affect HS will be included in the primary analysis by assigning non-response at subsequent timepoints. Multiple imputation and non-response imputation will be used to handle certain other types of missing data, analogously to the primary endpoint.
	Population Level Summary	Improvement in HS flare occurrence (Yes/No)
Change in DLQI from baseline to Week 12	Treatment Condition of Interest	izokibep versus placebo
	Population of Interest	Subjects with HS who meet all inclusion/exclusion criteria
	Variable of Interest	DLQI after 12 weeks of treatment
	Intercurrent Event	Treatment policy strategy, in general, with all subjects included in the analysis regardless of treatment discontinuation, concomitant medication/rescue medication, protocol deviations, or other actions
	Population Level Summary	Mean change from baseline in DLQI
AN count of 0, 1, or 2 at Week 12	Treatment Condition of Interest	izokibep versus placebo
	Population of Interest	Subjects with HS who meet all inclusion/exclusion criteria and with baseline Hurley Stage II
	Variable of Interest	Percentage of subjects achieving AN count of 0, 1, or 2 at Week 12
	Intercurrent Event	Treatment policy strategy, in general, with all subjects included in the analysis regardless of treatment discontinuation, concomitant medication/rescue medication, protocol deviations, or other actions. Subjects who receive antibiotic therapy that could affect HS will be included in the primary analysis by assigning non-response at subsequent timepoints. Multiple imputation and non-response imputation will be used to handle

		certain other types of missing data, analogously to the primary endpoint.
	Population Level Summary	Response Rate of AN count of 0, 1, or 2 at Week 12 (Yes/No)
	Treatment Condition of Interest	izokibep versus placebo
	Population of Interest	Subjects with HS who meet all inclusion/exclusion criteria and have a baseline numeric rating scale (NRS) ≥ 4
	Variable of Interest	Change in NRS score after 12 weeks of treatment
Change in pain score from baseline in NRS Patient Global Assessment of Skin Pain at its worst at Week 12	Intercurrent Event	Hybrid estimand, with treatment policy strategy used for most ICEs and hypothetical strategy used to account for use of prohibited pain medications due to non-HS-related pain, when taken near a visit. All pain scores after such use of prohibited pain medication (within 28 days of start date of pain medication) will be omitted from the dataset and replaced via multiple imputation in a model analogous to that used for multiple imputation of the primary endpoint. Additional details of multiple imputation described in Section 9.6.4 . If prohibited pain medication is used for HS purposes, then any visit within 28 days of the start date of the pain medication will be imputed as NRI. Multiple imputation and NRI will be used to handle other types of missing data, analogously to the primary endpoint.
	Population Level Summary	Response rate, reduction in NRS scores, specifically, at least a 3 point reduction from baseline in NRS in Patient Global Assessment of Skin Pain at its worst, at Week 12 (Yes/No)

6.9 Exploratory Endpoints

The exploratory endpoints are listed below. Due to the decision to write an abbreviated CSR, many exploratory endpoints defined in the protocol have been removed (See Section 5 Changes in the Analysis Specified in the Protocol):

- HiSCR75 at Weeks 2, 4, 8, 16, 32
- HiSCR90 at Weeks 2, 4, 8, 16, 32
- HiSCR100 at Weeks 2, 4, 8, 16, 32
- HiSCR50 at Weeks 2, 4, 8, 16, 32
- AN count of 0, 1, or 2 at Weeks 4, 8, 16, 24, 32
- Change in NRS Patient Global Assessment of Skin Pain at its worst in subjects with baseline NRS ≥ 4 at Weeks 4, 8, 16, 24, 32
- HS flares through Weeks 4, 16 and 52
- Change from baseline to Weeks 4, 8, 16, and 24 in DLQI
- Trough plasma concentrations of izokibep at collected timepoints
- ADAs

6.10 Safety Endpoints

6.10.1 Study Drug Exposure and Compliance

The subjects' exposure to study drug will be calculated separately for Week 16, and Week 52.

The number of doses administered per subject will count the number of administrations of each study drug until Week 16 and until Week 52. A partial dose in CRF will be treated as a half dose.

The duration of exposure will summarize the total time in days while taking study drug. The duration of exposure will be calculated, separately, for Period 1 and the full study period: date of last dose of study drug (prior to Week 16/52) – date of first dose of study drug (Day 1/Week 0) +1 .

For subjects who continue into Period 2, the Period 1 duration calculation will be derived with a slightly different formula: date of Week 16 dose – date of first dose of study drug. If the subject is missing the Week 16 dose but subsequent dosing was done, then 112 days will be imputed for the duration in Period 1.

An additional summary will be provided for Period 2 duration, which will summarize the total time in days taking the study drug in Period 2. The duration of exposure will be calculated as the date of last dose of study drug – date of first dose of study drug in Period 2 (Week 16 for most subjects) + 1.

If the date of first dose(Day 1/Week 0) is missing, then the date of dispense will be used. If the date of dispense is not available, but there is evidence of the subject taking at least 1 dose of the drug, then the date of randomization will be used.

Study drug compliance is defined as the number of doses that were taken relative to the number of doses that should have been taken as per the protocol for the planned duration of treatment exposure. Compliance to study treatment (%) will be calculated as follows for each subject at Week 12 and Week 16:

At Week 16:

$$\frac{\text{number of doses taken from Day 1 until Week 16}}{\text{number of doses expected to be taken from Day 1 until Week 16}} * 100\%$$

At Week 52 (Period 1 + Period 2, Total Study):

$$\frac{\text{number of doses taken from Day 1 until Week 52}}{\text{number of doses expected to be taken from Day 1 until Week 52}} * 100\%$$

At Week 52 (Period 2):

$$\frac{\text{number of doses taken from Week 16 until Week 52}}{\text{number of doses expected to be taken from Week 16 until Week 52}} * 100\%$$

The number of doses expected to be taken by Week 16 is 16, by Week 52 is 52, and by Week 52 (Period 2 only) is 36.

The calculated percentage compliance will be categorized at Week 16, Week 52 (Period 1 + Period 2, Total Study), and Week 52 (Period 2) as:

- < 80% compliance
- ≥ 80% compliance

6.10.2 Adverse Events

All AEs recorded on the CRF will be coded using the latest MedDRA dictionary around the time of Database Lock and classified as either AEs or TEAEs as follows:

- TEAEs in Period 1 are defined as:
 - Any adverse event with a start date/time after the first administration of study drug in the Treatment Period until the date/time of the Week 16 dose administration.
 - If the subject discontinued study treatment prior to taking the Week 16 dose, then 28 days from last dose of study drug administration will be used as the upper limit of the time-period, or
 - If a subject does not have treatment discontinuation prior to Week 16 dose and is missing the Week 16 dose and all subsequent doses, then the study day 112 will be used as the upper limit of the time-period, or
 - In the case of the subject missing Week 16 dose and continuing treatment in the study, the date/time of the first dose of drug in Period 2 will be used as the upper limit of the time-period
 -
 -
- TEAEs in Period 2
 - Events with start date and time after the start of administration of Period 2 treatment and up to 4 weeks after the end of the Treatment Period, or events with start date and time prior to the start of administration of Period 2 treatment whose severity worsens on or after the start of administration of Period 2 treatment and up to 4 weeks after the last dose of study treatment.
 - For subjects who receive treatment in period 2, TEAEs with start date after the start of period 2 will be assigned to period 2 only, not to period 1
- Treatment-emergent SAE are TEAEs that are indicated as Serious = "Yes".

- The relationship between a TEAE and treatment is assessed as related or not related. Treatment-related TEAEs are TEAEs that are indicated as “related to treatment”. If relationship to treatment is missing or unknown, then the TEAE is considered “related to treatment”.
- TEAEs leading to discontinuation of treatment are TEAEs where the “Action Taken with study treatment” = “Drug Withdrawn”
- Assessment of AE severity will be based on CRF AEs form. TEAEs with missing severity will be included in the counts as severe (Grade 3) unless the TEAE has an outcome of fatal; in that case, the TEAE with missing severity will be included in the counts as death (Grade 5).

6.10.2.1 *Injection Site Reaction*

Injection Site Reaction (ISR) is defined as

- Any adverse event where “Please check if this event is an injection site reaction” is checked “Yes” or MedDRA High Level Term = “injection site reactions”.
 - ISRs are mapped to a particular injection/visit based on the following logic:
 - If the ISR occurs on the day of an injection after administration of treatment or prior to the date/time of the next injection, it should be attributed to the visit where the latest injection occurred.
 - If the ISR occurs after administration of treatment at a particular visit and additional injections do not occur, then the ISR should also be attributed to the visit where the latest injection occurred.

6.10.2.2 *Adverse Event of Special Interest (AESI)*

The following AESIs will be included:

- Candida infection
- Inflammatory bowel disease
- Suicidal ideation
- Malignancies
- Major adverse cardiovascular and cerebrovascular events (MACE) (cerebrovascular accident and transient ischemic attack, non-fatal myocardial infarction or unstable angina, and cardiovascular death)
- Tuberculosis
- Infections (opportunistic, serious, or fungal only)
- Cytopenias (anemia, neutropenia, lymphopenia, monocytopenia, thrombocytopenia)
- Systemic hypersensitivity reaction

Adverse events of special interest will be identified manually. After all data are entered into the database, a list of all unique preferred terms (PTs) will be generated. ACELYRIN pharmacovigilance and clinical development representatives will review the list and determine which are TEAEs of special interest in each category listed above. This determination will be documented in a memo, signed and dated before database lock for the final analysis and stored in the study trial master file. The memo will specify the subjects and preferred terms to be included as AESIs, including justification for including or excluding events as appropriate. The database will not be locked until the memo is finalized and signed.

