6.2.5 Treatment Period

Data collected on Day 1 will be assigned to the Treatment Period unless the time (HH:MM) of data collection and time (HH:MM) of randomization are both recorded, and the data collection time is before the time of randomization. In this case, the assessment will be assigned to the Screening Period.

If the time (HH:MM) of data collection is not recorded but the protocol and/or CRF includes an instruction to the effect that all Day 1 assessments are to be performed prior to randomization, the data collected at Day 1 will be assigned to the Screening Period. However, adverse events and concomitant

medications starting on Day 1, will be assigned to the Treatment Period, unless the time (HH:MM) demonstrates otherwise. Adverse events occurring within 4 weeks of the last dose of study drug will also be assigned to the Treatment Period. Adverse events occurring > 4 weeks after the last dose of study drug will be assigned to the “Safety Follow-up Period”.

The Treatment Period will be defined as the time from the date/time of randomization to 1 week after the last dose or when the subject completes their End of Treatment visit. Adverse events that occur within 4 weeks of the last dose of study drug will be attributed to the Treatment Period as well.

Treatment Period will also be divided into 2 periods, Period 1 and Period 2:

- Period 1 is the placebo-controlled period, and will start at the date of randomization and end at Week 16 when Week 16 assessments are completed and before administration of study drug in Period 2 (at or after Week 16 dose date/time). If a subject discontinues study drug prior to Week 16 and continues to attend visits without treatment through Week 16 (e.g. eCRF visit or analysis visit Week 8, Week 12, Week 16), then these visits’ results will be considered in Period 1, and should be included in efficacy/safety summaries.
- Period 2 will start at the time of first administration of study drug at or after Week 16 and end at Week 56 or early termination/end of treatment visit. If a subject discontinued study drug prior to Week 16 and continues to attend visits without treatment after Week 16 (e.g. eCRF visit or analysis visit Week 20, 24, etc.), then these visits’ results will be considered in Period 2 and should be included in efficacy/safety summaries.

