The Safety Follow-up Period will start after completion of the End of Treatment visit (either Week 52 or EOT for subjects who discontinue treatment) or 8 days after the last dose of study drug (for subjects who don’t complete the End of Treatment visit). Adverse events that occur within 4 weeks of the last dose of treatment will not be assigned to the Safety Follow-up Period (rather, they will be assigned to the Treatment Period, either Period 1 or Period 2), but any adverse events after that time will be assigned to the Safety Follow-up Period. All other data collected in the defined Safety Follow-up Period will be assigned to it as stated.

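### The Period 1 TEAE window stops at study day 112 for subjects with no discontinuation before the Week 16 dose and no dose from then on, short of the SAP's own 4-week post-dose window

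*SAP*

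**What the plan says.** SAP 6.10.2 ends the Period 1 TEAE window at the Week 16 dose and then gives rules for subjects who miss that dose. Two of them concern subjects who never receive Period 2 treatment.

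- Discontinued before the Week 16 dose: "If the subject discontinued study treatment prior to taking the Week 16 dose, then 28 days from last dose of study drug administration" is the upper limit.
- Not discontinued before it: the rule covers anyone who "is missing the Week 16 dose and all subsequent doses, then the study day 112 will be used as the upper limit".

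A third rule, for subjects who miss the Week 16 dose but resume later, uses the first Period 2 dose and is not at issue.

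SAP 6.2.5 takes a single line on AEs after the last dose: "Adverse events occurring within 4 weeks of the last dose of study drug will also be assigned to the Treatment Period". It repeats this from the other side: "Adverse events that occur within 4 weeks of the last dose of treatment will not be assigned to the Safety Follow-up Period", and adds that they go to Period 1 or Period 2. Protocol 8.3.1 collects AEs until 4 weeks after the last dose.

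**The concern.** Two subjects with the same last dose can have different TEAE windows, depending only on whether a discontinuation before the Week 16 dose is recognised. The shorter window falls well inside the 4 weeks that the SAP elsewhere treats as the Treatment Period and that the protocol collects.

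Stopping at the crossover visit may itself be related to an event, so the truncated days are not obviously unimportant. The TEAE tables also carry more weight than usual here. Under SAP section 5, the abbreviated report will not summarise clinical laboratory data, ECGs, vital signs or physical examinations, although SAP 9.8.3.1 keeps a liver-function summary.

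**Working it through.** **Inputs**

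- Day numbering: randomization is Day 1 (SAP 6.2.1), so the Week k dose is nominally on Day 7k + 1.
- Dosing window: ±3 days (Protocol 1.3, footnote a).
- Window limits: study day 112, or last dose plus 28 days (SAP 6.10.2).
- Treatment Period rule for AEs: 4 weeks, that is 4 × 7 = 28 days, after the last dose (SAP 6.2.5).

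**The plan's own figure.** 16 × 7 = 112. This matches the scheduled day for Week 16 in SAP Tables 1 and 2, so Day 112 is the nominal end of the placebo-controlled period.

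**Effect on an affected subject.** With last dose on day d, the days counted after the dose are 112 − d. The 28-day limit is d + 28, and the days lost are (d + 28) − 112.

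| Last dose | Day d | Days counted after dose | 28-day limit | Days lost |
|---|---|---|---|---|
| Week 13 | 92 | 20 | Day 120 | 8 of 28 (29%) |
| Week 14 | 99 | 13 | Day 127 | 15 of 28 (54%) |
| Week 15 | 106 | 6 | Day 134 | 22 of 28 (79%) |

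For Week 15 with the ±3-day window, d runs from 103 to 109. Between 9 and 3 days are then counted and 19 to 25 are lost (68% to 89%). If Week k is taken as Day 7k, as in SAP Table 1, d = 105: 7 days are counted and 21 are lost (75%). The two rules agree only for a last dose on Day 84 (112 − 28). Any later last dose loses days.

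**Whether another output recovers the events**

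- Period 1 TEAE tables: no, because the window closed at Day 112.
- Period 2 TEAE tables: no. A Period 2 TEAE is defined from the start of Period 2 treatment (SAP 6.10.2), and SAFP2 requires a Period 2 dose (SAP Table 6).
- Total-study tables: these combine Periods 1 and 2 for the safety set (SAP 9.8.2). The SAP gives no separate total-study TEAE definition, so on its text the events are absent here too.
- Serious-TEAE listing: no, because treatment-emergent SAEs are defined as a subset of TEAEs (SAP 6.10.2).
- All-AE listing: yes, with a flag for TEAE status (SAP 9.8.2).

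**Who falls under the Day 112 rule.** SAP Table 3 counts a subject with a dose on or after Week 15 as having completed treatment through Period 1. Its category for discontinuing treatment within Period 1 requires no such dose. A programmer who takes the condition in SAP 6.10.2 from those flags would put every subject last dosed at Week 15 under Day 112. One who reads discontinuation from the End of Treatment form could put most of them under the 28-day rule. The SAP does not say which is meant.

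**The case against.** The strongest reply is that the affected group may be nearly empty. This SAP defines the final analysis, run after everyone has completed or discontinued treatment. By then, a subject with no dose from Week 16 on has stopped, and on a plain reading belongs under the 28-day rule. Day 112 would be only a fallback for a missing or late record. That may be how it works out, but Table 3 points the other way for a Week 15 last dose, so the group cannot be taken as empty. If it is meant to be empty, nothing is lost by aligning the limit.

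A second reply is that SAP 6.2.5 assigns AEs to periods while SAP 6.10.2 defines treatment emergence, and the AE listing shows the two as separate attributes. An AE could therefore be in the Treatment Period without being a TEAE. This is fair as far as it goes. But the SAP gives no reason for the divergence, the neighbouring rule uses 28 days, and the AE summary tables are built on TEAEs.

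The Period 1 definition also ends in two empty bullets. Whether text is missing there cannot be settled from the copy reviewed.

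Three stronger readings are tempting and are not supported.

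- A reader might infer that every subject whose last dose was Week 15 loses 22 days. One recognised as discontinued before the Week 16 dose keeps the full 28 days, to Day 134. Nor must an affected subject have been dosed at Week 15.
- A reader might say that longer treatment brings an earlier cut-off, by setting a Week 14 discontinuer (Day 127) against a Week 15 non-discontinuer (Day 112). That changes discontinuation status as well as dose. Among discontinuers the limit moves later, from Day 127 to Day 134; under the other rule it is Day 112 for both.
- A reader might infer that the events vanish from the report. They remain in the all-AE listing.

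**Conclusion.** The point holds for subjects with no discontinuation before the Week 16 dose who take neither that dose nor any later one. Their Period 1 TEAE window is shorter than the one SAP 6.2.5 implies and shorter than the one given to discontinued subjects. At nominal dosing days, 22 of 28 post-dose days are lost after a Week 15 last dose and 15 of 28 after a Week 14 last dose.

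The number of such subjects is not in the documents. A percentage of the 250 planned subjects assumed to stop after Week 15 would not supply it, because that would also count those who keep 28 days. The rule applies to both arms, and nothing in the documents shows which arm it would affect more. The loss from the total-study tables rests on there being no separate TEAE definition for them. It is worth correcting because the rule as written can under-count post-dose TEAEs and serious TEAEs.

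**What to change.** In the Day 112 bullet of SAP 6.10.2, replace the fixed day with the limit already used in the bullet above it: "then 28 days from last dose of study drug administration will be used as the upper limit of the time-period". Every subject with no Period 2 dose then has the same window, in line with SAP 6.2.5, and the unclear boundary with Table 3 no longer affects the result. The cost is one line of SAP text and one line of derivation code. No new data are needed, because Protocol 8.3.1 already collects AEs over these 4 weeks.
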